2.2.3 Clinical activity and Safety of ibrutinib

Ibrutinib was tested in a phase I, multicenter, open-label, dose escalation study in patients with recurrent NHL.(14) The objectives included studying the safety profile of ibrutinib, identifying the maximum tolerated dose (MTD) and optimal dosing schedule, and characterizing efficacy, pharmacokinetics, and pharmacodynamics. A minimum of 6 subjects per cohort received 1 of 5 escalating dose levels of ibrutinib between 1.25 and 12.5 mg/kg for 28 consecutive days in a 35-day cycle. There was a pre-specified objective of escalating 3 dose levels above that which achieved full BTK occupancy based on the fluorescent probe assay.

A total of 66 patients were evaluated in this study. Two additional cohorts received a continuous ibrutinib dose of 8.3 mg/kg without a 7-day rest and a fixed continuous dose of 560 mg/day. Full BTK occupancy was achieved with doses ≥2.5 mg/kg/day. A dose of 12.5 mg/kg/day was the highest dose cohort evaluated. There were 2 dose-limiting toxicities (DLTs) (Grade 2 neutropenia [2.5 mg/kg/day] and Grade 3 hypersensitivity [8.3 mg/kg/day]) in separate cohorts. The maximum tolerated dose (MTD) of ibrutinib in subjects with B-cell malignancies was not established in this study. Five of 15 subjects with DLBCL (33%) achieved objective responses, 2 CRs and 3 partial responses (PRs). The median

time on treatment was 8 weeks (range: 2 to 98 weeks). Median PFS was 2.5 months (range: 0.7 to 4.6 months) and the median follow-up time was 3.5 months (range: 0.8 to 22.5 months).

A subsequent phase I/II, multicenter, open-label, and single-arm study in subjects with rel/ref DLBCL was performed. (15)In order to determine whether ibrutinib had subtype specificity subjects enrolled were retrospectively analyzed into cohorts by subtype, either activated B-cell like (ABC) versus germinal B-cell like (GCB). Subtype analysis was performed by gene expression profiling (GEP). In this study all subjects received a starting dose of ibrutinib at 560 mg/day. The objectives of this study included the determining the safety of this dosing regimen and an assessment of efficacy of ibrutinib in DLBCL. Eighty subjects were enrolled and evaluable for response. The overall response rate (ORR) was 25% (20/80 subjects). In the ABC subtype, ORR was 37% (14/38 subjects; Only 1 PR (5%) was observed in the 20 patients retrospectively determined to be of GCB subtypes. Thus, while the 2 subgroups were retrospectively assigned, ibrutinib may be less active in rel/ref DLBCL, GCB subtype.

The most common adverse reactions (>=25%) in pts with B cell malignancies (MCL, CLL, WM) were thrombocytopenia, neutropenia, diarrhea, anemia, fatigue, musculoskeletal pain, bruising, nausea, upper respiratory tract infection and rash.

2.3 Rationale for combination of Umbralisib and Ibrutinib

B-cell lymphomagenesis is known to be a result of aberrant signaling through the B-cell receptor (BCR). Several models have highlighted specific checkpoints that appear to be regulators of downstream signal propagation leading to abnormal nuclear transcription within the lymphocyte leading to either anti-apoptosis or a proliferative advantage.(5) A better understanding of the BCR signaling pathway has led to several small molecule inhibitors entering clinical practice as single agents. As described above, umbralisib and ibrutinib have shown safety and activity in DLBCL. Also important is the significant lack of evidence for cumulative toxicity as single agents to date. For umbralisib it has been postulated that the novel structure unlike other PI3K inhibitors has led to its lack of a significant toxicity profile making it a pairable novel oral agent.

propose that attacking the aberrant BCR signaling pathway at separate nodes may be an important mechanism to overcome the chemorefractory DLBCL regardless of cell of origin.

Alterations in single agent safety profiles can arise after an established MTD and often lessen the enthusiasm for such novel combinations and again question the durability of a continuous use paradigm. Nevertheless, combinations of oral novel-novel agents continue to emerge.(16) However, an example of unforeseen toxicities was highlighted in a recent report with lenalidomide, idelalisib (PI3-K inhibitor), and rituximab in patients with relapsed/refractory CLL and indolent NHL.(17) A sepsis-like syndrome was reported in 4 patients and resulted in stopping of these early phase studies without achieving a maximal tolerated dose (MTD).

It is well established dogma that a MTD is the objective in phase I studies. However, this only reports dose limiting toxicities during the initial cycle of therapy when further cumulative toxicities may be seen in subsequent cycles that limits the

utility of a regimen. Therefore, in paradigms were long-term safety and tolerability is paramount and furthermore needed to balance with objective responses, a phase IIa study can be employed to not only provide this tolerability signal or cumulative toxicity events (CTEs), but be informative for future studies that lead to appropriately powered and better informed phase II or phase III studies.

Page 12 of 65

As discussed above the phase I/lb study (NCT #02006485) with ublituximab and umbralisib in rel/ref CLL and NHL continues to accrue. An amendment to this protocol allowed for the addition of ibrutinib at 560 mg daily to UTX (fixed at 900 mg) in addition to increasing doses of umbralisib. To date, safety data on umbralisib is notable for no episodes of hepatotoxicity reported with umbralisib as a single agent or in combination with ublituximab (doublet), or with ibrutinib (triplet).(10, 16, 18) In the 12 rel/ref DLBCL patients treated with umbralisib and UTX whom were eligible for response 5 patients had obtained a response and two had a PET/CT confirmed complete responses. Sixteen patients have been enrolled into the triplet regimen without a DLT in the NHL cohorts. The 800 mg dose level of umbralisib has been enrolled and completed without a DLT. Early responses have been seen in multiple NHL subtypes.

Given the safety of the umbralisib as a single agent, in the doublet and the triplet cohorts in combination with the early efficacy signal reported we propose to further explore the safety and tolerability of an all oral regimen of ibrutinib and umbralisib in patients with rel/ref DLBCL who have relapsed post-transplant or have been determined to be ineligible or unsuitable for transplant at the full doses of umbralisib (800 mg) and Ibrutinib (560 mg) in a single center open label phase IIa study.

Section 3.0 Eligibility Criteria:

3.1 Inclusion Criteria

- 1. Histologically confirmed Diffuse Large B-cell Lymphoma (DLBCL) or transformed DLBCL
- 2. Disease status defined as:
 - a. Patients with relapsed or refractory DLBCL that has relapsed post-transplant or that has been determined to be ineligible or unsuitable for transplant. Patients must have received at least one prior systemic therapy.
- 3. Patients must have measurable (≥ 1.5 cm) or evaluable disease. Baseline measurements and evaluations must be obtained within 21 days of registration to the study. Abnormal PET scans will not constitute evaluable disease, unless verified by CT scan or other appropriate imaging. Measurable disease must have at least one objective measurable disease parameter. A clearly defined, bi-dimensionally measurable defect or mass measuring at least 1.5 cm in diameter on a CT scan will constitute measurable disease. Proof of lymphoma in the liver is required by a confirmation biopsy. Skin lesions can be used as measurable disease provided bi-dimensional measurements are possible.
- 4. Adequate organ system function, defined as follows:
 - a. Absolute neutrophil count (ANC) $\geq 1.0 \times 10^9$ /L
 - i. By automated or manual review, whichever is greatest
 - b. Platelets $\geq 100 \times 10^9$ /L:
 - i. Unless due to bone marrow infiltration then eligible if platelets > 50 x 10⁹/L)
 - c. Total bilirubin \leq 1.5 x upper normal limit if documented hepatic involvement with lymphoma, or \leq 5 x upper normal limit if history of Gilbert's Disease.
 - d. Alanine aminotransferase (ALT) and aspartate aminotransferase (AST) ≤2.5 x ULN if no liver involvement or ≤5 x the ULN if documented liver involvement
 - e. Creatinine ≤2.0 mg/dL OR calculated creatinine clearance ≥50 mL/min (as calculated by the Cockcroft-Gault method, Appendix B)
- 5. ECOG performance status ≤2 or expected survival duration of > 2 months (Appendix C)
- 6. Patients must be ≥19 years of age (the age of consent in Nebraska)
- 7. Ability to swallow and retain oral medication
- 8. Women must not be pregnant or breast-feeding due to teratogenic effects of therapy.
 - a. All female patients of child-bearing potential must have a negative serum pregnancy test within 2 weeks prior to treatment to rule out pregnancy
 - b. Pregnancy testing is not required for post-menopausal or surgically sterilized women.
- 9. Male and female patients of reproductive potential must agree to follow accepted birth control measures throughout the study period and for 30 days after the last dose of either study drug for females and 3 months after the last dose of study drug for males.
- 10. Patient must be able to adhere to the study visit schedule and other protocol requirements.

Page 13 of 65

- 11. Patient must be aware of the neoplastic nature of his/her disease and willingly sign (or their legally-acceptable representatives must sign) an informed consent document indicating that they understand the purpose of and procedures required for the study, including biomarkers, and are willing to participate in the study.
- 12. No serious disease or condition that, in the opinion of the investigator, would compromise the patient's ability to participate in the study

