Definitions for clinical response for patients with lymphoma are from the Lugano Response Criteria for Malignant Lymphoma.(24) Lymph node measurements should be taken from CT or the CT portion of the PET/CT. Measurement of lymphadenopathy will be determined by adding the sum of the products of the maximal perpendicular diameters of measured lesions (SDP). Measurable extranodal disease should be assessed in a manner similar to that for nodal disease. For these recommendations, the spleen is considered nodal disease. Disease that is only assessable, such as diffuse infiltration of an organ such as the stomach, bone marrow, peripheral blood, liver, lungs, or bowel by lymphoma without a discrete mass would constitute assessable, but not measurable, disease (eg, Lymph node or tumor mass greater than 1.5 cm in at least one dimension by physical exam, splenic enlargement, if the spleen is palpable, at least 3 cm below the left costal margin) will be recorded as present or absent only, unless, while an abnormality is still noted by imaging studies or physical examination, it is found to be histologically negative.

Response is based on PET/CT (Deauville 3 or less) or CT alone if CR is achieved by PET/CT.

Response criteria, modified from the Lugano response criteria. DLBCL is considered FDG avid.

Response Category	Definition	Nodal Masses	Spleen, liver	Bone Marrow
CR	Disappearance of all evidence of disease.	Mass of any size permitted if PET negative	Not palpable, nodules disappeared	Infiltrate cleared on repeat biopsy; if indeterminate by morphology, immunohistochemistry should be negative
PR Regression of measurable		≥50% decrease in SPD of up to 6 largest dominant	≥50% decrease in SPD of nodules (for single nodule	Irrelevant if positive prior to therapy; cell type should be specified

	disease and no new sites	masses; no increase in size of other nodes and one or more PET positive at previously involved site	in greatest transverse diameter); no increase in size of liver or spleen		
SD	Failure to attain CR/PR or PD	PET positive at prior sites of disease and no new sites on CT or PET			

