Relapse/ Progressive disease	Any new lesion or increase by ≥50% of previously involved sites from nadir	Appearance of a new lesion(s) > 1.5 cm in any axis, ≥ 50% increase from nadir in SPD of more than one node, or ≥50% increase in longest diameter of a previously identified node > 1 cm in short axis. The lesions referred to above are required to be PET positive.	> 50% increase from nadir in the SPD of any previous lesions	New or involvement	recurrent

Abbreviations: CR, complete remission; FDG, [18F] fluorodeoxyglucose; PET, positron emission tomography; CT, computed tomography; PR, partial remission; SPD, sum of the product of the diameters; SD, stable disease; PD, progressive disease.

6.2 Complete Response (CR):

- 6.2.1 Complete disappearance of all detectable clinical evidence of disease and definitely disease-related symptoms if present before therapy.
- 6.2.2 DLBCL is a FDG-avid lymphoma: when the PET scan was positive before therapy, a post-treatment residual mass of any size is permitted as long as it is PET negative.
- 6.2.3 The spleen and/or liver, if considered enlarged before therapy on the basis of a physical examination or CT scan, should not be palpable on physical examination and should be considered normal size by imaging studies, and nodules related to lymphoma should disappear. However, determination of splenic involvement is not always reliable because a spleen considered normal in size may still contain lymphoma, whereas an enlarged spleen may reflect variations in anatomy, blood volume, the use of hematopoietic growth factors, or causes other than lymphoma. Similarly, other organs considered to be enlarged before therapy due to involvement by lymphoma, such as liver and kidneys, must have decreased in size.
- 6.2.4 If the bone marrow was involved by lymphoma before treatment, the infiltrate must have cleared on repeat bone marrow biopsy. The biopsy sample on which this determination is made must be UNMC IRB#345-16 Protocol Version 4.2 Dated 07Oct2019

adequate (with a goal of > 20 mm unilateral core). If the sample is indeterminate by morphology, it should be negative by immunohistochemistry. A sample that is negative by immunohistochemistry but that demonstrates a small population of clonal lymphocytes by flow cytometry will be considered a CR until data become available demonstrating a clear difference in patient outcome.

6.3 Criteria for Partial Response (PR). The designation of PR requires all of the following:

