- 6.3.1 At least a 50% decrease in sum of the product of the diameters (SPD) of up to six of the largest dominant nodes or nodal masses. These nodes or masses should be selected according to all of the following:
 - they should be clearly measurable in at least 2 perpendicular dimensions
 - if possible they should be from disparate regions of the body
 - they should include mediastinal and retroperitoneal areas of disease whenever these sites are involved
- 6.3.2 No increase should be observed in the size of other nodes, liver, or spleen.
- 6.3.3 Splenic and hepatic nodules must regress by ≥50% in their SPD or, for single nodules, in the greatest transverse diameter.
- 6.3.4 With the exception of splenic and hepatic nodules, involvement of other organs is usually assessable and no measurable disease should be present.
- 6.3.5 Bone marrow assessment is irrelevant for determination of a PR if the sample was positive before treatment. However, if positive, the cell type should be specified (eg, large-cell lymphoma or small neoplastic B cells). Patients who achieve a CR by the above criteria, but who have persistent morphologic bone marrow involvement will be considered partial responders.
 - When the bone marrow was involved before therapy and a clinical CR was achieved, but with no bone marrow assessment after treatment, patients should be considered partial responders.
- 6.3.6 No new sites of disease should be observed.
- 6.3.7 For patients with PET scan was positive before therapy, the post-treatment PET should be positive in at least one previously involved site.

6.4 Criteria for Stable Disease (SD):

- 6.4.1 A patient is considered to have SD when he or she fails to attain the criteria needed for a CR or PR (see above), but does not fulfill those for progressive disease (see below).
- 6.4.2 The PET should be positive at prior sites of disease with no new areas of involvement on the post-treatment CT or PET.

6.5 Relapsed Disease (after CR)/Progressive Disease (after PR, SD):

Lymph nodes should be considered abnormal if the long axis is more than 1.5 cm regardless of the short axis. If a lymph node has a long axis of 1.1 to 1.5 cm, it should only be considered abnormal if its short axis is more than 1.0. Lymph nodes $\le 1.0 \times 1.0$

6.5.1 Appearance of any new lesion more than 1.5 cm in any axis during or after completion of therapy, even if other lesions are decreasing in size. Increased FDG uptake in a previously unaffected site

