An efficacy-stopping rule is also in place for the combination. After testing the combination on 12 patients, the trial will be terminated if </= 1 patients respond. If the trial goes on to the second stage and not discontinued due to the CTE stopping rules prior to, a total of 24 patients will be studied. If the total number responding is less than or equal to five, the regimen will be rejected. This follows a Simon two-stage design for efficacy following a minimax design with the following parameters: overall response rate for a poor regimen of 0.01, overall response rate for a good regimen of 0.31, a type I error of 0.20 and power of 80%.

Efficacy measures which will be determined include ORR, TTR, DOR, and PFS. ORR is defined as the percentage of patients achieving a best response of CR/CR, PR at any disease assessment time point. TTR is defined as the time or number of cycles between study registration and documentation of first response (CR/Cru, or PR). DOR is defined as the time or number of cycles between documentation of first response and progression, change of therapy, death, or date of last contact (if still alive without progression). PFS is defined as the time between study registration and documented progression or death if no progression was observed.

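### Patients with evaluable-only disease may enter, but partial regression of non-marrow disease that is only assessable cannot be scored PR, so the responder count in the Simon rule may run low

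*Combined protocol and SAP*

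**What the plan says.** - **Entry (3.1, criterion 3; repeated in Appendix E).** "Patients must have measurable (≥ 1.5 cm) or evaluable disease". There is no cap on evaluable-only patients. The only limit on the term is negative: "Abnormal PET scans will not constitute evaluable disease, unless verified by CT scan or other appropriate imaging".
- **Recording (6.1).** Diffuse infiltration of an organ without a discrete mass is classed as assessable but not measurable. It "will be recorded as present or absent only", unless a persisting abnormality proves histologically negative.
- **PR (6.3).** The list is conjunctive: "The designation of PR requires all of the following". Item 6.3.1, which covers masses as well as nodes, asks for "At least a 50% decrease in sum of the product of the diameters (SPD) of up to six of the largest dominant nodes". Item 6.3.4 covers other organs without any graded threshold: "With the exception of splenic and hepatic nodules, involvement of other organs is usually assessable and no measurable disease should be present".
- **Marrow exceptions (6.3.5).** Patients who otherwise meet CR "but who have persistent morphologic bone marrow involvement will be considered partial responders". The same holds for a clinical CR with baseline marrow involvement and no repeat marrow assessment.
- **Decision rule (10.0).** Efficacy is assessed in the whole cohort. The trial stops if at most 1 of the first 12 patients responds. At 24: "If the total number responding is less than or equal to five, the regimen will be rejected". CR and PR both count as response.

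**The concern.** The entry rule and the response rules do not cover the same patients. Someone with diffuse infiltration of liver, lung, stomach or bowel and no discrete mass can be enrolled, yet has no diameters from which to show a 50% fall. If the infiltrate regresses substantially but remains visible, it is still recorded as present, and no item in 6.3 turns that into a PR.

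Response is a secondary endpoint, but it drives a stopping rule and a rejection rule with small integer cut-offs. An evaluable-only patient sits in the 12 or the 24 with the ordinary PR route closed. For this kind of disease the error in ORR can go only one way, towards too few responders and too ready a rejection.

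There is a related gap for progression. Growth of an existing unmeasured infiltrate has no size criterion in 6.5.

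**Working it through.** **1. Which outcomes are open to a patient with nothing to measure**

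| Outcome | Open? | Basis |
|---|---|---|
| CR | Yes | 6.2: disappearance of disease; no SPD needed |
| PR, marrow disease, otherwise CR | Yes | 6.3.5, two cases |
| PR, partial regression of a non-marrow infiltrate | No | 6.3.1 is mandatory; 6.3.4 gives no threshold; 6.3.7 only asks that PET stay positive at a prior site |
| PD by growth of the existing infiltrate | No size criterion | 6.5.2 and 6.5.3 need measured increases |
| PD by other routes | Yes | 6.1: global deterioration without a prior CR or PR; response table and 6.5.1: new lesion, new or recurrent marrow involvement |

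Death also counts, as treatment failure and as a PFS event. No PET-based rule fills the PR gap: the only uptake threshold written in Section 6 (Deauville 3 or less) defines CR.

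**2. Reproducing the plan's power**

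Inputs from Section 10.0: n1 = 12, stop at ≤1; N = 24, reject at ≤5; good-regimen rate 0.31; stated power 80%.

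Power(p) = Σ over x = 2 to 12 of P[Bin(12, p) = x] × P[Bin(12, p) ≥ 6 − x].

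At p = 0.31 this gives 0.781, with a stage-1 stopping probability of 0.074. That is within 2 points of the stated 80%.

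**3. Effect of evaluable-only patients**

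Assumptions, none of them figures set by the plan for this purpose:
- The evaluable-only share f is 5% to 20%, which is 1.2 to 4.8 of 24.
- These patients truly respond at 0.31.
- Only their CRs are scored, at a CR share of 0.40. The Introduction reports 2 CRs among 5 DLBCL responders to ibrutinib alone, and 2 among 5 for umbralisib with ublituximab.

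Scored rate = 0.31 × [(1 − f) + 0.40 f]. At f = 0.10: 0.31 × (0.90 + 0.04) = 0.291.

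Expected responders lost = 24 × 0.31 × 0.60 × f. At f = 0.10: 0.45.

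| f | Scored ORR | Lost of 24 | Stage-1 stop | Power |
|---|---|---|---|---|
| 0 | 0.310 | 0 | 0.074 | 0.781 |
| 5% | 0.301 | 0.22 | 0.084 | 0.752 |
| 10% | 0.291 | 0.45 | 0.095 | 0.721 |
| 20% | 0.273 | 0.89 | 0.120 | 0.652 |

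As an extreme bound, if none of these patients' responses counted, power would be 0.732, 0.676 and 0.547 at 5%, 10% and 20%. The protocol does not imply this, because CR stays open.

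**4. The borderline result of exactly six responders**

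At 0.31, the chance of passing stage 1 and finishing with exactly six true responders is 0.139. For the final decision to reverse there, at least one of the six must be an evaluable-only PR, with probability 1 − (1 − 0.60 f)^6:
- f = 5%: 0.139 × 0.167 = 0.02
- f = 10%: 0.139 × 0.310 = 0.04
- f = 20%: 0.139 × 0.536 = 0.07

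**The case against.** The strongest reply is that the effect may be nil. The protocol gives no evaluable-only share, and if every enrolled patient has a measurable lesion nothing changes. Safety is the primary objective and efficacy is described as preliminary, so admitting evaluable disease is a defensible choice in a 24-patient safety study. This stands, and it limits the weight of the point. It does not remove the mismatch, because the rule still acts on the responder count.

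Other parts of the reply correct readings that go too far:

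- **That such patients can never be PR.** A reader might infer this from 6.3.1 alone, but 6.3.5 grants PR without SPD in two marrow cases. Repeat marrow biopsy is optional under 5.10.1, so a marrow-only patient called clinical CR without a repeat biopsy would be scored PR, possibly too generously. The downward bias is shown only for non-marrow disease.
- **That progression cannot be shown and PFS is therefore lengthened.** New lesions, marrow involvement, global deterioration and death still count. Only growth of an existing unmeasured infiltrate lacks a criterion, and no effect on PFS has been quantified.
- **That 0.14 is the chance of a reversed decision.** It is the chance of exactly six responders. Reversal at that count is about 0.02 to 0.07 under the same assumptions.

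Two further points are fair. The protocol never expressly equates evaluable (3.1) with assessable (6.1), although it offers no third class. Section 6.1 also lists a not-evaluable category and does not say whether that or SD would apply. In neither case would the patient be a responder.

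**Conclusion.** The concern holds in limited form. Partial regression of non-marrow, assessable-only disease cannot be scored PR under 6.3, while criterion 3 admits such patients and Section 10.0 gives no ground for leaving them out of the 12 and 24. Any resulting bias in ORR from this disease is downward.

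Its size is unknown. With a share of 5% to 20%, a true ORR of 0.31 and a CR share of 40%, power falls by 3 to 13 points (0.781 to between 0.752 and 0.652). At the lower end the expected loss is about a fifth of one responder, and with no such patients it is zero. The CR share rests on two sets of five responders from other regimens. This should be corrected because a stated rule misclassifies responders and the remedy is cheap. It is not evidence that the regimen would be wrongly rejected.

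**What to change.** Make the entry and response rules agree, in one of two ways:

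1. Require at least one bi-dimensionally measurable lesion (nodal, extranodal or skin), either for entry (criterion 3 and Appendix E) or only for the patients counted in the Simon rule. The second form keeps evaluable-only patients for the safety endpoint.
2. Keep the entry rule, and add to 6.3 and 6.5 a PR and a PD rule for assessable-only disease, based on the PET/CT already scheduled after cycles 2, 4, 6, 9 and 12.

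In either case, define evaluable in terms of the Section 6.1 classes, state in Section 10.0 how any such patients count in the 12 and the 24, and report ORR with and without them.

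The cost is wording in the eligibility, response and statistics sections. A few patients would not be enrolled or not counted for response, or a separate PET-based rule would apply to them. No scans are added.
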